1.1 Background

Plantar ulcers are a serious complication in leprosy and diabetes globally resulting in hospitalization, disability, and amputation. Continued pressure over the vulnerable site leads to ulcers and then impedes ulcer healing. Therefore, in addition to removal of infection off-loading the ulcer area is essential to heal the ulcer. The current proposed feasibility plus study is based on removable off-loading walker boot fitted with soft insole which can be easily applied with limited training and may allow the patient to continue their essential daily routine activities. We will test the feasibility and acceptability of using this device and set the scene for a potential trial to test the effectiveness of this device type in reducing ulcer development and ulcer complications in community setting.

1.2 Objectives

Primary objectives (feasibility):

- Measure adherence rates with the off-loading device versus standard care (provision of footwear with MCR insole).
- ii) Observe the acceptability of the device in terms of comfort and acceptability.
- iii) Elicit views on a potential randomised control trial with effectiveness outcomes.

Secondary (plus) objectives

- i) Set the scene for a future RCT by piloting trial methods and measurements.
- ii) To observe ulcer prevalence at baseline
- iii) To observe the healing rates in interventions vs control patients

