1.9 Qualitative interview

User experience on removable walker boot will be explored through semi-structured walking interviews. An estimate of fifteen patients in each site, sampled purposively, will be asked about their experiences of using the device. In the interviews we will seek to elicit reasons for adherence and non-adherence to removable walker.

2 Background

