4.8 Qualitative study

User experience on removable walker boot will be explored through semi-structured walking interviews. A random sample of patients in the intervention arm of the trial, stratified by gender and age group, will be sampled. Recruitment will be undertaken when the participant joins the trial. The walking interview will be arranged for 2-4 weeks after they receive the walker boots to allow time for the interviewee to experience living with the walker boot. We will recruit until data saturation – estimate fifteen patients from each site. The researcher will arrange to spend up to half a day with each patient. They will be asked to show the researcher around their household and locality as far as they are able to reach without transport and during this walk, explain how use or not of the device affects their ability to undertake daily routines and mobility. They will be asked about their experiences of using the device, challenges they meet in using the device and how they negotiate challenges related to using removable walker boots. They will also be asked about what modifications can be made to improve its effectiveness in off-loading at the same time as to improve adherence. The researcher will audio record the interview and take field notes. Interviews will be transcribed and translated. Fieldnotes will be typed up and

expanded after the walking interview. Data from all sites will be combined for thematic analysis, whilst paying attention to differences in context for interviewees from the different sites.

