6.4 Appendix 4: Qualitative interview guide

After explaining the purpose of the walking interview and informed consent open ended questions will be asked to explore their lived experiences of using the off-loading device and facilitators and barriers to use of such devices.

The walking route will be no more than in and around the home or other place where participant performs daily routine activities.

- What is your experience on using this off-loading device?
- What made you to wear this device continuously (at least while walking)
 - Explain all reasons that made you to wear this device.
- What are the difficulties that you faced while using this device?
 - Explain the individual difficulties you faced
- How easy or difficult for you to do your essential routine activities with device on
- Would you suggest any modifications to improve the effectiveness of the device to heal ulcer at the same time improve adherence to it

7 References

2. Meima A, van Veen NH, Richardus JH. Future prevalence of WHO grade 2 impairment in relation to incidence trends in leprosy: an exploration. Trop Med Int Health. 2008;13(2):241-6.

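### Primary objective iii, views on a future RCT, is served by no interview question or questionnaire item; the interviews cover only the device and only boot-arm patients

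*Protocol*

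**What the plan says.** Sections 1.2 and 3 of the protocol give three primary feasibility objectives: adherence, acceptability of the device and, third, to "Elicit views on a potential randomised control trial with effectiveness outcomes". Piloting of trial methods is listed separately, as a secondary objective.

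The qualitative component is described in three places.

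- Section 4.8 gives its purpose: "User experience on removable walker boot will be explored through semi-structured walking interviews". It gives the sample: "A random sample of patients in the intervention arm of the trial, stratified by gender and age group, will be sampled". It gives the content: "They will be asked about their experiences of using the device, challenges they meet in using the device", followed by how patients deal with those challenges and what changes to the boot would help. It gives the size: "We will recruit until data saturation – estimate fifteen patients from each site".
- Section 1.9 gives the aim as "In the interviews we will seek to elicit reasons for adherence and non-adherence to removable walker", and describes the sample differently: "An estimate of fifteen patients in each site, sampled purposively, will be asked about their experiences of using the device".
- Appendix 4 gives the guide. It opens with "What is your experience on using this off-loading device" and goes on to reasons for wearing the device, difficulties, daily activities and suggested modifications.

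Section 5.1.3 says that a refusal is noted and no data are kept on the person, but that the reasons for refusing are recorded. Section 5.1.4 provides a withdrawal form for those who stop contributing follow-up data.

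**The concern.** A primary objective needs at least one stated source of information. Objectives i and ii have theirs: pedometers for adherence, and QUEST 2.0 and the interviews for acceptability. Objective iii appears in the list and is not taken up again in the outcomes, the qualitative methods, the analysis plan or the forms.

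The study exists to prepare a larger effectiveness trial. Whether patients accept being randomised, accept allocation to MCR footwear, tolerate the measurement schedule and would join a larger trial are all things the designers of that trial would want to know. If participants are not asked while they are in the study, the answers cannot be recovered from pedometer, satisfaction or healing data. A report on RCT acceptability would then have to be inferred from how boot users feel about the boot, which is a different question.

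**Working it through.** The plan states no figure on this point, so the check is to trace objective iii to each source of participant information in the protocol.

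| Source | Where | What it covers | Directed at views on an RCT? |
|---|---|---|---|
| Main outcomes | 1.8, 4.6.5 | Adherence, QUEST satisfaction, healing | No |
| Analysis plan | 4.9 | Steps, satisfaction score, healing rate | No |
| Case record form | Appendix 3 | Demographic and clinical data, pedometer readings, ulcer measurements, adverse events | No |
| QUEST 2.0 | Appendix 3 | Size, weight, adjustment, safety, durability, ease of use, comfort, effectiveness of the device | 0 of 8 items |
| Interview content | 1.9, 4.8 | Device use, challenges, modifications, reasons for adherence or non-adherence | No |
| Interview guide | Appendix 4 | Experience, reasons for wearing, difficulties, daily activities, modifications | 0 of 5 main questions |
| Refusal reasons | 5.1.3 | Why a person declined this study | Adjacent; decliners only, not linked to the objective |
| Withdrawal form | 5.1.4 | Notice of withdrawal from follow-up | Adjacent; not described as eliciting views |

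QUEST was never meant to serve objective iii. It is listed only because it is the one questionnaire participants complete. The weight of the finding rests on the interview rows.

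Who is interviewed:

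- Planned interviews: 15 per site × 2 sites = about 30 (an estimate, since recruitment runs to saturation).
- Arm size: 150 randomised 1:1 (sections 4.4 and 4.6.3), so 150 / 2 = about 75 per arm.
- Boot arm interviewed: 30 / 75 = 40%. Control arm interviewed: 0 / 75.

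Cost of moving some interviews to the control arm with the total held at about 30:

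- 4 per site: 4 / 15 = 27% of the boot-arm interviews (8 of 30).
- 5 per site: 5 / 15 = 33% (10 of 30).

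Sampling method: section 1.9 says purposive and section 4.8 says random, stratified by gender and age group. Both refer to the same interviews, with the same estimate of fifteen per site. A purposive sample picks informants for what they can tell; a stratified random sample does not. Both statements cannot hold for one sample.

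**The case against.** A reader might infer that the study collects nothing at all relevant to objective iii. The documents do not support that. Refusal reasons are recorded despite the rule that no data are kept on decliners, and they concern a randomised comparison of the same boot with the same footwear. They therefore bear on whether a larger trial would be acceptable. What remains is that they come only from people who said no, and that no section connects them to the objective.

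The interviews are semi-structured, use open questions and may last up to half a day, so a patient could well mention randomisation or the pedometers. That is true, but nothing in section 4.8 or Appendix 4 prompts it, and a primary objective should not depend on a chance remark.

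The objective does not say whose views are meant. Clinicians, or the patient representatives who sit on the Study Management Group (section 5.5.1), might be intended. No process for eliciting their views is described, so this widens the gap rather than closing it. It does weaken a second tempting inference, that control participants are the group whose views matter most. The protocol ranks no group, and that would be a reviewer's opinion.

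Finally, an analysis plan held elsewhere would not normally supply an interview guide. The sample and the guide are fixed in this protocol.

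**Conclusion.** The point holds in a limited form. No stated interview question or questionnaire item serves primary objective iii: 0 of 5 main guide questions address it, and the interviews are confined to the boot arm. The only adjacent material, chiefly the refusal reasons, is partial and unlinked. Followed as written, the study would leave one of three primary objectives without an answer from those who took part.

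This assumes that Appendix 4 as printed is the whole guide and that the views sought include those of participants. If other respondents were meant, the defect is that neither they nor a method of asking them is named. Participant safety, the sample size and the other two primary objectives are not affected. The change should be made before the interviews start, because the gap cannot be repaired after they are done.

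The conflict over sampling between sections 1.9 and 4.8 is real but separate, and adds nothing to the weight of this point.

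**What to change.** 1. Add three or four questions to Appendix 4 and name the topic in section 4.8: acceptability of being randomised and of being allocated to MCR footwear; the burden of pedometers, photographs and weekly visits; willingness to join a larger trial; and which outcomes matter to the patient.
2. State that the refusal reasons recorded under section 5.1.3 will be summarised under objective iii, and state whose views the objective covers.
3. If the sponsor does not want this, reword or drop objective iii in sections 1.2 and 3.
4. Optionally, hold a few short control-arm interviews. With the total kept at about 30, 4 to 5 per site would remove 27% to 33% of the boot-arm interviews, which could weaken the evidence on device acceptability. Adding them on top avoids that loss but costs extra field time.
5. Separately, give one sampling method in sections 1.9 and 4.8.

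Items 1 and 2 cost a few minutes per interview, a short summary of data already planned, and an amendment reported to the ethics committees under section 5.2. Sample size, randomisation and treatment are unchanged.

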1.3 Design

A community based, randomized feasibility plus trial.

1.4 Study participants

Patients aged 18 years and above with loss of sensation (inability to feel monofilament of 10 grams) and plantar ulcer in the foot due to leprosy or diabetes. Patients with multiple or bilateral ulcers will be included alongside those with just one ulcer.

1.5 Intervention group

Removable walker boot will be applied to off-load the ulcer area(s). This removable nature facilitates daily dressing of the ulcer and monitoring its progress. This also allows patient mobility to carry out essential activities of daily living. The details of the intervention are described below.

1.6 Control group

The current standard of care provided in the community, Micro-cellular rubber footwear.

1.7 Follow-up

The patient will be followed up for 8 weeks and photographs of ulcers will be taken at baseline and after every until the ulcer heals or at 8 weeks, whichever is earlier, to measure the ulcer area and to record the pedometer values.

1.8 Outcomes

The main outcome measures are; 1) Adherence to removable walker boot which will be measured using pedometer; one placed inside the walker boot and second on patient's wrists as a watch/ in pocket. 2) User satisfaction which will be measured using standard questionnaire. 3) Ulcer healing which we will measure the healing of ulcer time to (complete epithelisation of ulcer) and measure the rate of healing both assessed from photographs by masked observers.

1.9 Qualitative interview

User experience on removable walker boot will be explored through semi-structured walking interviews. An estimate of fifteen patients in each site, sampled purposively, will be asked about their experiences of using the device. In the interviews we will seek to elicit reasons for adherence and non-adherence to removable walker.

2 Background

2.1 Problem of plantar ulcers in leprosy and diabetes

Plantar ulcers are a serious complication in leprosy and diabetes globally resulting in hospitalization, disability, and amputation. About 26 million people worldwide annually have a diabetic foot ulcer with another 130 million at risk of diabetic neuropathy.(1) Though the actual burden of ulcers in leprosy is unknown, it is estimated that over 3 million people are living with disability due to leprosy and that 20-50% of patients with peripheral neuropathy due to leprosy will experience ulcers.(2, 3)

The prevalence of diabetes is 8.4% in India(4) and 8.5% in Nepal.(5) These figures are higher than the global prevalence of 6.3%.(6) About one third of diabetic patients develop foot ulcers in their lifetime.(1) While the lifetime incidence of foot ulcers in leprosy is not known, an ongoing cross-sectional study on prevalence of disabilities due to leprosy has shown that over 30% of patients with an anesthetic foot presented with plantar ulcer. Foot ulcers reduce patient mobility, social interaction, and health-related quality of life. The treatment of foot ulcers increases substantial burden on healthcare.(7, 8) Therefore, proper management and expedited healing of foot ulcers is important to limit the burden of ulcer care.

2.2 Challenges in management of plantar ulcers in leprosy and diabetes

The role of pressure on the sole of foot in the pathogenesis of neuropathic plantar ulcer is well established.(9, 10) Continued pressure over the vulnerable site leads to ulcers and then impedes ulcer healing.(11) Therefore, in addition to removing any infection, an effective way to promote healing of ulcers is rest - either complete bed rest, which is rarely possible or, commonly, rest to the affected part using an off-loading method.(11, 12)

The gold standard alternative to rest is use of total contact cast with Bohler irons.(12, 13, 14, 15) The total contact cast method is considered superior as there is a forced compliance since patients cannot remove the cast (16), but is not favored by the patients and clinicians alike. Clinicians find total contact cast unfavorable because of the associated skin abrasions and iatrogenic ulcers. Prolonged use of total contact casts has been associated with muscle atrophy and reduced bone density.(17) A practical problem with the total contact case is that it requires a skilled technician to apply and requires constant monitoring.(18) The expertise is fast disappearing and poorly applied plaster casts will cause more ulcers than they heal.(14, 19) Ulcer specialists and their patients are therefore seeking for a more flexible, less cumbersome method than a total contact cast. These alternatives include 1) Knee high removable off-

loading walker boot, 2) Ankle high removable off-loading walker boot and 3) Footwear with soft insole (micro-cellular rubber) with off-loading provision using orthosis(20).

The advantage of all these removable off-loading methods is that they can be used with minimal training and in community settings. They are less bulky, cause problems in carrying daily routine activities.(21) The main difference between removable and total contact cast is that with the latter, adherence to treatment is the patients choice as they can remove the device, and thus, patient adherence to using these devices has a large impact on healing. Therefore, understanding the factors that influence patients' adherence to using removable off-loading devices is vital to improving the use and effectiveness of off-loading treatments and the healing outcomes for people with plantar ulcers.

In this study we will generate pilot data to inform a larger clinical trial to evaluate the impact of removable offloading device on adherence and ulcer healing. The current proposed feasibility plus study is based on removable off-loading walker boot fitted with soft insole. This device can be easily applied with limited training and may allow the patient to continue their essential daily routine activities. We will test the feasibility and acceptability of using this device and set the scene for a potential trial to test the effectiveness of this device type in reducing ulcer development and ulcer complications in community setting.

2.3 Current use of off-loading methods to heal plantar ulcers in LMICs

Studies in high income countries show adherence with removable off-loading devices ranging from 28% to 60% (≥80% of daily steps/time) .(22) The situation may be very different in low and middle income countries (LMIC).

We conducted a literature review with the aim of understanding the effectiveness of total contact casts compared to removable off-loading devices for plantar ulcers in patients with diabetes mellitus or leprosy in LMIC. We sought to understand the predictors of adherence to using off-loading devices to heal plantar ulcers to diabetes mellitus or leprosy and any difference in healing rates. Our database search yielded 250 potentially relevant abstracts. These abstracts were reviewed by two researchers. We included 8 studies in the review, 5 randomized control trials; and 3 case series. The majority of the studies identified focused on people with diabetes (n=6)(23, 24, 25, 26, 27, 28) and only one study focused on people affected by leprosy (29) . The final study, a case series,1 included a mixed population of people affected by leprosy, diabetes and meningomyelocele.(30) The majority of the studies (n=5)

used total contact cast (25, 27, 30, 31, 32) as off-loading method and found it to be superior to other techniques (modified ankle foot orthosis (26), removable ankle high cast, (33) and standard dressing (25, 32). Adherence to cast use has been reported to be a major concern but none of the studies measured adherence objectively.(25, 26, 27, 29, 30) None of the studies used removable off-loading devices of the type we propose to test in this study. As a result of difficulties in procurement and support, the great majority of people in LMICs with neuropathic ulcers receive none of the above devices and are provided with footwear with a soft insole of Micro-cellular rubber.

We have an ongoing study on the use of off-loading removable walker boot with soft insole to off-load ulcer area in hospital practice where it is being compared to a total contact cast in patients with non-infected plantar ulcer due to leprosy (Trial registration number: CTRI/2022/06/043568). In this proposed feasibility trial, we want to extend this method to a community where patients with plantar ulcer due to leprosy or diabetes can be treated at home after they are assessed and provided with such a device in a one-off healthcare facility visit prior to initiation of intervention. Our study community is rural where weight bearing is a particular problem because farming is the main occupation.

3 Objectives

Primary objectives (feasibility):

- Measure adherence rates with the off-loading device versus standard care (provision of footwear with MCR insole).
- ii) Observe the acceptability of the device in terms of comfort and acceptability.
- iii) Elicit views on a potential randomised control trial with effectiveness outcomes.

Secondary (plus) objectives

- i) Set the scene for a future RCT by piloting trial methods and measurements.
- ii) To observe ulcer prevalence at baseline.
- To observe healing rates in interventions vs control patients (see sample size below to inform size calculations). We have experience in making the above measurements in hospital (34) and the community (35) and the NIHR RIGHT Leprosy INSTIL studies.

4 Methodology

The protocol for the feasibility study has been developed according to SPIRIT guideline and in accordance with recommendations on reporting standards of studies on prevention and management of diabetic foot ulcers.(36)

4.1 Study setting

Community setting in Champa district, Chhattisgarh, India and satellite clinics of Anandaban Hospital in Nepal. Through the ongoing work of the National Institute of Health Research, UK, funded research project working on several projects including cross-sectionals study to estimate the prevalence of ulcers and disabilities due to leprosy and implementation and evaluation of self-care program in Champa district. Through this project we have a cohort of patients with plantar ulcer due to leprosy in the Champa district, Chhattisgarh Champa. They will be screened for eligibility to participate in this feasibility study. In Nepal, we will be linking in with satellite clinics run by TLM Nepal in different provinces such as Anandaban hospital Patan Clinic at Lalitpur, Biratnagar clinic at Koshi Hospital, Biratnagar and Butwal clinic at Lumbini Provincial Hospital, Butwal to identify potential participants.

4.2 Study design

A community based, randomized feasibility plus trial.

4.3 Study population

The study populations will consist of patients with non-complicated plantar ulcer in an insensate foot due to leprosy or diabetes. These ulcers will have no visible infection, no involvement of underlying structures, absence of slough and with sloping and healing edge. They will be screened for eligibility to be included in the study and then informed consent obtained.

